#### If the answer is No:

Follow the process described in "Potential Hy's Law Criteria Met" in this Appendix for reporting PHL as an SAE.

#### If the answer is Yes:

Determine whether there has been a significant change in the subject's condition compared with the previous occurrence of PHL. Note: A "significant" change in the subject's condition refers to a clinically relevant change in any of the individual liver biochemistry parameters (ALT, AST, or total bilirubin) in isolation or in combination or a clinically relevant change in associated symptoms. The determination of whether there has been a significant change will be at the discretion of the investigator; this may be in consultation with the study medical monitor if there is any uncertainty.

- If there is no significant change, no action is required.
- If there is a significant change, follow the process described in "Potential Hy's Law Criteria Met" in this Appendix for reporting PHL as an SAE.

## LABORATORY TESTS

 Table 13 represents the standard comprehensive list of follow-up tests that may aid in assessing

 PHL/HL.

Test results used to assess PHL/HL should be recorded on the appropriate eCRF.

Additional standard chemistry	GGT							
and coagulation tests	LDH							
	Prothrombin time							
	INR							
Viral hepatitis	IgM anti-HAV							
	IgM and IgG anti-HBc							
	HBsAg							
	HBV DNA							
	IgM and IgG anti-HCV							
	HCV RNA							
	IgM anti-HEV							
	HEV RNA							
Other viral infections	IgM and IgG anti-CMV							
	IgM and IgG anti-HSV							
	IgM and IgG anti-EBV							
Alcoholic hepatitis	Carbohydrate deficient transferrin (CD-transferrin)							
Autoimmune hepatitis	Antinuclear antibody (ANA)							
	Anti-Liver/Kidney Microsomal Ab (Anti-LKM)							
	Anti-Smooth Muscle Ab (ASMA)							
Metabolic diseases	alpha-1-antitrypsin							
	Ceruloplasmin							
	Iron							
	Ferritin							
	Transferrin							
	Transferrin saturation							

# Table 13 Laboratory Tests to Aid in Assessing Potential Hy's Law / Hy's Law

#### Reference

FDA Guidance for Industry (issued July 2009). Drug-induced liver injury: premarketing clinical evaluation. http://www.fda.gov/downloads/Drugs/GuidanceComplianceRegulatoryInformation /Guidances/UCM174090.pdf

1 INTRODUCTION

The purpose of this statistical analysis plan (SAP) is to provide details of the planned statistical analyses that have been outlined within Protocol Amendment 6 for Study ACE-LY-005, which is entitled “A Phase 1b/2 Proof-of-Concept Study of the Combination of ACP-196 and Pembrolizumab in Subjects with Hematologic Malignancies” dated 14 March 2019. Any changes to the methods described in the final SAP will be documented in the clinical study report (CSR). Hereafter, acalabrutinib (a generic name for ACP-196) will be used in place of ACP-196 in this document.

Separate reports will be generated for pharmacokinetic (PK) and pharmacodynamics (PD) data.

2 OBJECTIVES

2.1 Primary Objectives

[figure not shown]
- To characterize the safety profile of acalabrutinib and pembrolizumab in subjects with hematologic malignancies.

2.2 Secondary Objectives

- To evaluate the activity of acalabrutinib and pembrolizumab as measured by response rate, duration of response, progression-free survival, overall survival, and time to next treatment.

2.3 Exploratory Objectives:

CCI

3 STUDY OVERVIEW

3.1 Study Design

This is a Phase 1b/2, open-label, nonrandomized study that will be conducted in 2 stages. In the first stage, Part 1 of the study will determine the safety and preliminary

efficacy of acalabrutinib and pembrolizumab in a limited group of B-cell malignancies. In the second stage, Part 2 allows for possible expansion cohorts into a wider range of B-cell malignancies, and Part 3 (enrolled concurrently with Part 2) will evaluate the combination in subjects with myelofibrosis (MF).

Part 1

Six subjects will be enrolled to receive acalabrutinib in combination with pembrolizumab. If the combination is safe with ≤ 1 dose-limiting toxicity (DLT) (6-week observation period) in the first 6 subjects, the cohort will be expanded up to 24 subjects to obtain additional safety information and to assess the efficacy of the combination.

Part 1 of the study will include adult subjects with the following disease types:

- Non-GCB diffused large B-cell lymphoma (DLBCL)
- Follicular lymphoma (FL)
- Chronic lymphocytic leukemia (CLL)/Small lymphocytic lymphoma (SLL)

Part 2

Part 2 consists of expansion groups of up to 30 subjects per histology provided the safety and efficacy results from Part 1 of the study indicate that further evaluation of the combination is warranted. The possible expansion groups for Part 2 could include adult subjects with the following disease types:

- Non-GCB DLBCL
- GCB DLBCL
- Richter syndrome (RS)
- Mantel cell lymphoma (MCL)
- Non-Hodgkin lymphoma (iNHL)
 - FL
 - Waldenström Macroglobulinemia (WM)
 - CLL/SLL
- Multiple Myeloma (MM)
- Other B-cell malignancy (including but not limited to: Hodgkin's lymphoma, Burkitt lymphoma, marginal zone lymphomas, mediastinal large B-cell lymphoma, and hairy cell leukemia)

Under Amendment 3 of this protocol, subjects with MCL or iNHL (including FL, WM, and CLL/SLL) are no longer enrolled. Under Amendment 4, subjects with RS are no longer enrolled.

Part 3

Part 3 includes up to 30 subjects with primary MF, post-polycythemia vera MF, or postessential thrombocythemia MF with thrombocytopenia or anemia. Part 3 will run in parallel with Part 2. Subjects with MF will receive a run-in of 6 weeks of acalabrutinib alone.

Subjects who are demonstrating a clinically meaningful response, in the opinion of the investigator, may continue on acalabrutinib monotherapy; those who are not will be treated with combination therapy with acalabrutinib and pembrolizumab.

In Part 3, safety and response data will be reviewed after the initial 12 subjects have completed 24 weeks of treatment (i.e., the Week 25 visit) or have discontinued treatment before Week 25. The first 12 subjects will be evaluated regardless of the length of treatment with acalabrutinib alone or in combination with pembrolizumab. If < 2 subjects who received acalabrutinib monotherapy or the combination with pembrolizumab have achieved a response of “clinical improvement” or better, the MF group will not be expanded. The decision to expand the study is multifactorial and will take into consideration the nature and quality of response, safety, and evolving competitive landscape. If the safety and response data indicate that further evaluation is warranted, up to 18 additional subjects with MF (for a total of up to 30 subjects) will be treated on the same adaptive regimen as was given to the first 12 subjects.

Under Amendment 3 of this protocol, Part 3 is closed to enrollment.

All Parts

Treatment with acalabrutinib may be continued until disease progression or an unacceptable drug-related toxicity occurs as defined in the protocol. Treatment with acalabrutinib can continue until the end of trial, defined as 48 months after the last subject is enrolled.

Subjects who are still on treatment at the end of the study and deriving clinical benefit from acalabrutinib treatment may be eligible to enroll in a separate rollover study. Treatment with pembrolizumab may continue for 24 months (103 weeks) from first dose of pembrolizumab, provided subjects are tolerating the drug and not progressing. In addition, pembrolizumab treatment can end for subjects with confirmed complete remission (CR) (or stringent complete remission [sCR] for MM) if treatment has been

administered for at least 24 weeks and 2 doses of pembrolizumab have been administered after confirmation of CR/sCR. Subjects who have **confirmed** progressive disease will come off treatment. Note: If there is uncertainty regarding whether there is cancer progression, the subject may continue study treatment and remain under close observation (e.g., evaluated at 4- to 8-week intervals) pending confirmation of progression. In particular, transient worsening of disease during temporary interruption of study therapy (eg, for drug related toxicity or intercurrent illness) may not indicate disease progression. In such circumstances, and if medically appropriate, subjects may resume therapy and relevant clinical, laboratory, and/or radiographic assessments should be done to document whether tumor control can be maintained or whether actual disease progression has occurred.

All subjects will have bone marrow biopsy, hematology, chemistry, thyroid, and urinalysis safety panels performed at screening. Once dosing commences (Day 1), all subjects will be evaluated for safety, including serum chemistry, hematology, and thyroid function tests, once weekly for the first 8 weeks, followed by a Week 10 visit and then every 3 weeks thereafter (every 6 weeks thereafter for thyroid function tests) through Week 103. For subjects who discontinue pembrolizumab at Week 103, the Week 103 visit will be followed by Week 106 and Week 109 visits, at which time, the investigator will determine eligibility to continue single-agent acalabrutinib treatment. Subjects remaining on study treatment after Week 103 will have a Week 103 and Week 115 visit, and then visits for safety and tumor response assessments every 24 weeks starting at Week 127 through 3 years (for subjects with CLL/SLL histologies) or 5 years (for subjects with non-CLL/SLL histologies [i.e., DLBCL/Hodgkin lymphoma]), and then every 52 weeks thereafter (all histologies).

Subjects who permanently discontinue pembrolizumab at any time during study participation must have a minimum of 2 consecutive study visits, 3 weeks apart, after the last dose of pembrolizumab for safety evaluation. The study visits will be scheduled as follows:

- For all subjects except MM and CLL subjects
 - If a subject discontinued pembrolizumab prior to completing 37 weeks on study and is on acalabrutinib alone, study visits will be held every 3 weeks until Week 37. After Week 37, study visits will be held every 12 weeks.

- If a subject discontinued pembrolizumab after completing 37 weeks on study and is on acalabrutinib alone, 2 consecutive study visits will be held 3 weeks apart (eg, Week 40 and 43), after which study visits will be held every 12 weeks.
- It is acknowledged that the discontinuation timepoint of pembrolizumab (if applicable) is unique per subject. To synchronize the every 12-week study visit schedule with the radiologic tumor assessment schedule, the first 2 study visits after pembrolizumab discontinuation should be 3 and 6 weeks after pembrolizumab discontinuation and then scheduled to align with the nearest radiological timepoint.
- For CLL subjects
 - If a subject discontinued pembrolizumab prior to completing 37 weeks on study and is on acalabrutinib alone, study visits will be held every 3 weeks until Week 37. After Week 37, study visits will be held every 12 weeks.
 - If a subject discontinued pembrolizumab after completing 37 weeks on study and is on acalabrutinib alone, study visits will be held every 12 weeks.
 - It is acknowledged that the discontinuation timepoint of pembrolizumab (if applicable) is unique per subject. To synchronize the every 12-week study visit schedule with the radiologic tumor assessment schedule, the first study visit should be scheduled to align with the nearest radiological timepoint. In addition, subjects who permanently discontinue pembrolizumab for any reason (eg, pembrolizumab toxicity, AE, or completing the 103-week course of pembrolizumab) and remain on acalabrutinib alone at any time during study participation must have a thyroid test done every 6 weeks for 6 months after pembrolizumab discontinuation. Thyroid testing may be discontinued at 6 months if 1) testing that was performed at 6 months was normal and 2) testing that was performed 6 weeks prior to the 6-month timepoint was normal (for a total of 2 consecutive normal test results). Otherwise, thyroid testing will continue as scheduled until 2 consecutive normal test results.

Refer to protocol Appendix 5 and Appendix 6 for a comprehensive list of study assessments and their timing.

3.2 Sample Size

In Part 1 (dose-limiting toxicity [DLT] review), enrollment of 6 subjects for DLT review is consistent with sample sizes used in oncology studies for determination of maximum toxicity dose (MTD). The trial employs the standard National Cancer Institute definition of MTD (dose associated with DLT in < 33.3% of subjects). Provided ≤ 1 DLT occurs during the DLT review, then expansion will occur in Part 1 to include up to 24 subjects in a select group of histologies. The safety and preliminary efficacy results from Part 1 will be used to determine opening Part 2 and Part 3 of the protocol.

In Part 2 (expansion groups), enrollment of 30 subjects offers the opportunity to determine if there is sufficient antitumor activity to warrant further development in the selected tumor types. An ORR of $\geq 20\%$ is considered the minimum value of potential interest in each of the selected indications. If < 2 subjects per cohort experience an objective response, the probability is > 0.90 that an ORR of $\geq 20\%$ will be excluded for that cancer. If 2 subjects in a group experience an objective response, the upper bound of a 1-sided exact binomial 90% CI = 16.8%.

In Part 3, safety and response data will be reviewed after the initial 12 subjects have completed 24 weeks of treatment (ie, the Week 25 visit) or have discontinued treatment before Week 25. The first 12 subjects will be evaluated regardless of the length of treatment with acalabrutinib alone or in combination with pembrolizumab. If < 2 subjects who received acalabrutinib monotherapy or the combination with pembrolizumab have achieved a response of “clinical improvement” or better, the myelofibrosis (MF) group will not be expanded. The decision to expand the study is multifactorial and needs to take into consideration the nature and quality of response, safety, and evolving competitive landscape. If the safety and response data indicate that further evaluation is warranted, up to 18 additional subjects with MF (for a total of up to 30 subjects) will be treated on the same adaptive regimen as was given to the first 12 subjects.

Table 3-1 shows the 2-sided exact 90% binomial CIs on the true response rate for the range of all possible values for the observed response rate in the initial group of 12 subjects.

Table 1. Two-Sided Exact 90% CIs for Response Rate in Initial Group in Part 3 (N=12)

Statistical Analysis Plan**Version 1.00 dated: 17 January 2020**

Responses, n	Response Rate, %	90%CI	
		Lower Bound	Upper Bound
0	0%	0%	22%
1	8%	0%	34%
2	17%	3%	44%
3	25%	7%	53%
4	33%	12%	61%
5	42%	18%	68%
6	50%	25%	75%
7	58%	32%	82%
8	67%	39%	88%
9	75%	47%	93%
10	83%	56%	97%
11	92%	66%	100%
12	100%	78%	100%

Abbreviation: CI = confidence interval.

If the MF group is expanded, enrollment of 30 subjects offers the opportunity to determine if there is sufficient antitumor activity to warrant further development in MF. A response rate (clinical improvement, PR, or CR) of $\geq 25\%$ within the sample size of 30 subjects with MF is considered the minimum value of potential interest in this highly unmet medical need population of MF patients with thrombocytopenia or anemia. To reject the null hypothesis of response rate $\leq 5\%$ in favor of an alternative hypothesis that the response rate is $\geq 25\%$, 30 subjects will preserve approximately 90% power to detect the difference at a 0.05 level of significance by 1-sided exact test for single proportion. Considering the planned expansion cohort size of 30 subjects, Table 3-2 shows the 2-sided exact 90% binomial CIs on the true response rate for the range of all possible values for the observed response rate.

Table 3-2. Two-Sided Exact 90% CIs for Response Rate in Expansion Cohorts in Part 2 and Part 3 (N=30)

Responses, n	Response Rate, %	90%CI	
		Lower Bound	Upper Bound
0	0%	0%	10%
1	3%	0%	15%
2	7%	1%	20%
3	10%	3%	24%
4	13%	5%	28%
5	17%	7%	32%
6	20%	9%	36%
7	23%	11%	39%
8	27%	14%	43%
9	30%	17%	47%
10	33%	19%	50%
11	37%	22%	53%
12	40%	25%	57%
13	43%	28%	60%
14	47%	31%	63%
15	50%	34%	66%
16	53%	37%	69%
17	57%	40%	72%
18	60%	43%	75%
19	63%	47%	78%
20	67%	50%	81%
21	70%	53%	83%
22	73%	57%	86%
23	77%	61%	89%
24	80%	64%	91%
25	83%	68%	93%
26	87%	72%	95%
27	90%	76%	97%
28	93%	80%	99%
29	97%	85%	100%
30	100%	90%	100%

Abbreviation: CI=confidence interval.

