	To characterize the safety profile of acalabrutinib and pembrolizumab in subjects with hematologic malignancies
	Secondary Objective:
	To evaluate the activity of acalabrutinib and pembrolizumab as measured by overall response rate (ORR), duration of response, progression-free survival (PFS), overall survival, and time-to-next treatment
	Exploratory Objectives:
	eci

Safety Parameters:	Type, frequency, severity, timing of onset, duration, and relationship to study drug of any treatment-emergent AEs or abnormalities of laboratory tests; serious AEs (SAEs); events of clinical interest (ECIs), or AEs leading to discontinuation of study treatment.
Pharmacodynamic and Biomarker Parameters:	CCI
Efficacy Parameters:	• ORR
	Duration of response
	Progression-free survival
	Overall survival
	Time-to-next treatment
	In addition, for Part 3 subjects with MF, an overall response will be defined as clinical improvement or better (clinical improvement, partial response [PR], or CR) as shown in Table 9. Under Amendment 3 of this protocol, Part 3 is closed to enrollment.
Sample Size:	Part 1: Up to 24 subjects
	Part 2: Up to 270 subjects
	Part 3: Up to 30 subjects
	Note: Under Amendment 3 of this protocol, Part 3 is closed to enrollment.
Inclusion Criteria:	
 
Part 1:
 
Diagnosis of non-GCB DLBCL or iNHL as documented by medical records and with histology based on criteria established by the World Health Organization (WHO). 
 
If a subject has DLBCL, it is characterized as de novo non-GCB DLBCL (Hans et al 2004; Choi et al 2009).
 
If the subject has iNHL, the histology shows one of the following subtypes: 
 
FL Grade 1, 2, or 3a
 
CLL/SLL
 
 
 
Prior treatment for lymphoid malignancy (applies to Part 1 and Part 2): 
 
If the subject has DLBCL, there is no curative option with conventional therapy and the prior treatment included
 
 
 

≥1 prior combination chemoimmunotherapy regimen (e.g., anthracycline based therapy with rituximab).

 
If the subject has MCL or iNHL, the prior treatment comprised any of the following:
 

 
≥1 regimen containing an anti-CD20 antibody administered for ≥2 doses, and/or
 

 
≥1 regimen containing ≥1 cytotoxic agent (e.g., bendamustine, chlorambucil, cyclophosphamide, cytarabine, doxorubicin) administered for ≥2 cycles, and/or
 

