	Note: In Part 3, subjects with MF will receive a run-in of 6 weeks of acalabrutinib alone (100 mg BID). Subjects who are demonstrating a clinically meaningful response, in the opinion of the investigator, may continue on acalabrutinib monotherapy; those who are not will receive combination therapy with acalabrutinib (100 mg BID) and pembrolizumab (200 mg Q3W) as described above. Under Amendment 3 of this protocol, Part 3 is closed to enrollment.
Concomitant Medications:	The concomitant use of strong inhibitors/inducers of CYP3A with acalabrutinib should be avoided when possible.
	The effect of agents that reduce gastric acidity (e.g., antacids or proton-pump inhibitors,) on acalabrutinib absorption was evaluated in a healthy volunteer study (ACE-HV-004). Results from this completed study indicate subjects should avoid the use of calcium carbonate-containing drugs or supplements for a period of at least 2 hours before and at least 2 hours after taking acalabrutinib. Use of omeprazole, lansoprazole or esomeprazole or any other proton-pump inhibitors while taking acalabrutinib is not recommended due to a potential decrease in study drug exposure. However, the decision to treat with proton-pump inhibitors during the study is at the investigator's discretion, with an understanding of the potential benefit to the subject's gastrointestinal condition and a potential risk of decreased exposure to acalabrutinib. Although the effect of H2-receptor antagonists (such as famotidine or ranitidine) on acalabrutinib absorption has not been evaluated, if treatment with an H2-receptor antagonist is required, the H2-receptor antagonist should be taken approximately 2 hours after an acalabrutinib dose.
Statistics:	Descriptive statistics (including means, standard deviations, and medians for continuous variables and proportions and confidence intervals [CIs] for discrete variables) will be used to summarize data as appropriate. Depending on Part 1 and the expansion cohorts opened in Parts 2
	and 3, a total of 6 to 324 evaluable subjects will be enrolled in this study. Under Amendment 4 of this protocol, the planned total enrollment is approximately 160 evaluable subjects.
	In Part 1 (DLT review), enrollment of 6 subjects for DLT review is consistent with sample sizes used in oncology studies for

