# 5.0 STATISTICAL METHODS OF ANALYSIS

# 5.1 GENERAL CONSIDERATIONS

Descriptive statistics (including means, standard deviations, and medians for continuous variables and proportions and CIs for discrete variables) will be used to summarize data as appropriate. As appropriate, analyses will be performed by cancer type or overall. Depending on Part 1 and the number of expansion cohorts opened in Parts 2 and 3, a total of 6 to 324 evaluable subjects will be enrolled in this study. Under Amendment 4 of this protocol, the planned total enrollment was approximately 160 evaluable subjects; enrollment was closed in May 2017 with a total of 161 evaluable subjects.

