### 5.2 SAMPLE SIZE JUSTIFICATION

In Part 1 (DLT review), enrollment of 6 subjects for DLT review is consistent with sample sizes used in oncology studies for determination of MTD. The trial employs the standard National Cancer Institute definition of MTD (dose associated with DLT in <33.3% of subjects). Provided ≤1 DLT occurs during the DLT review, then expansion will occur in Part 1 to include up to 24 subjects in a select group of histologies (as described in Section 3.0). The safety and preliminary efficacy results from Part 1 will be used to determine opening Part 2 and Part 3 of the protocol.

In Part 2 (expansion groups), enrollment of 30 subjects per group offers the opportunity to determine if there is sufficient antitumor activity to warrant further development in the selected tumor types. An ORR of  $\geq$ 20% is considered the minimum value of potential interest in each of

the selected indications. If <2 subjects per cohort experience an objective response, the probability is >0.90 that an ORR of  $\geq$ 20% will be excluded for that cancer. If 2 subjects in a group experience an objective response, the upper bound of a 1-sided exact binomial 90% CI=16.8%.

In Part 3, safety and response data will be reviewed after the initial 12 subjects have completed 24 weeks of treatment (i.e., the Week 25 visit) or have discontinued treatment before Week 25. The first 12 subjects will be evaluated regardless of the length of treatment with acalabrutinib alone or in combination with pembrolizumab. If <2 subjects who received acalabrutinib monotherapy or the combination with pembrolizumab have achieved a response of "clinical improvement" or better (see Table 9), the MF group will not be expanded. The decision to expand the study is multifactorial and needs to take into consideration the nature and quality of response, safety, and evolving competitive landscape. If the safety and response data indicate that further evaluation is warranted, up to 18 additional subjects with MF (for a total of up to 30 subjects) will be treated on the same adaptive regimen as was given to the first 12 subjects.

 Table 10 shows the 2-sided exact 90% binomial CIs on the true response rate for the range of
 all possible values for the observed response rate in the initial group of 12 subjects.

Beenenees n	Response Rate, %	90%CI	
Responses, n		Lower Bound	Upper Bound
0	0%	0%	22%
1	8%	0%	34%
2	17%	3%	44%
3	25%	7%	53%
4	33%	12%	61%
5	42%	18%	68%
6	50%	25%	75%
7	58%	32%	82%

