9 STATISTICAL METHODS OF ANALYSIS

9.1 General Principles

Descriptive statistics will be used to summarize baseline demographic and disease characteristics, study drug administration, efficacy and safety outcomes. Descriptive summaries of discrete data will present the sample size and the incidence as a frequency and as a percentage. Descriptive summaries of continuous data will present

the sample size, group mean, standard deviation (SD), median, and range. Confidence intervals (CIs) may be included as appropriate.

Summary tables will be presented by disease types: CLL/SLL, MCL, WM, FL, GCB DLBCL, MM, non-GCB DLBCL, RICHTER's and Other (include unclassifiable DLBCL, double hit lymphoma, FL with transformation, mediastinal DLBCL, mediastinal gray zone lymphoma, non-hodgkin's lymphoma [NHL], non-mediastinal gray zone lymphoma, red pulp small B-cell lymphoma, triple hit high grade NHL, hodgkin's lymphoma, marginal zone lymphoma), unless otherwise stated.

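### The Part 2 statement that few responders exclude a 20% ORR is written for 30 subjects per group, but with 161 enrolled over nine disease groups it cannot hold in all nine

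*SAP*

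**What the plan says.** SAP 3.2 bases Part 2 on a fixed group size: "In Part 2 (expansion groups), enrollment of 30 subjects offers the opportunity to determine if there is sufficient antitumor activity". Protocol 5.2 makes the unit explicit: "enrollment of 30 subjects per group offers the opportunity to" judge whether further development is warranted. Both sections set an ORR of 20% as the minimum of interest in each indication. Both say that fewer than 2 responders in a cohort exclude such a rate with probability above 0.90, and both give 16.8% as the 1-sided exact 90% upper bound for 2 responders. The protocol synopsis gives the same rule for 2 or fewer responders. Precision for Part 2 is shown only at N=30 (Protocol Table 11, SAP Table 3-2).

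The design text treats 30 as a ceiling: "Part 2 consists of expansion groups of up to 30 subjects per histology". The synopsis allows "Part 2: Up to 270 subjects", which is nine groups of 30. Part 1 comes on top of that: after the first 6 subjects, "the cohort will be expanded up to 24 subjects".

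Enrolment was later cut. Under Amendment 4, "the planned total enrollment is approximately 160 evaluable subjects", and Protocol 5.1 reports that "enrollment was closed in May 2017 with a total of 161 evaluable subjects". The legend to Protocol Figure 4 says the myelofibrosis part was not opened, so the 161 are Part 1 and Part 2 subjects. The SAP, version 1.00, is dated 17 January 2020. It says "Summary tables will be presented by disease types: CLL/SLL, MCL, WM, FL, GCB DLBCL, MM, non-GCB DLBCL, RICHTER's and Other", which makes nine groups. It repeats the N=30 rationale and table and gives neither the total of 161 nor any group size.

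**The concern.** The exclusion statement is made for every cohort and carries no condition on the number treated. Its validity depends on that number: 1 responder in 30 is strong evidence against a 20% response rate, while 1 in 10 is weak evidence. By the date of the SAP, enrolment had been closed for more than two years at a total well short of nine groups of 30.

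A fixed responder count read against a small group would call an indication inactive more often than the plan says. A reader who takes SAP Table 3-2 as the precision of the smaller groups would also expect intervals narrower than the data can give.

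**Working it through.** **Inputs.** Total enrolled: 161 (Protocol 5.1). Disease groups: 9 (SAP 9.1). Part 1: 6 to 24 subjects (SAP 3.1); the number actually enrolled is not given. ORR of minimum interest: 20%. Bound: 1-sided exact 90% (SAP 3.2). Rule: fewer than 2 responders (SAP 3.2, Protocol 5.2) or 2 or fewer (synopsis). Assumption: each of the nine groups enrolled at least one subject.

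**Reproducing the plan at n=30.** The exact upper bound for x responders in n is the 0.90 quantile of Beta(x+1, n−x). For 2/30 it is 16.8%, as stated. With a true ORR of 20%, P(X≤1) = 0.0105 and P(X≤2) = 0.0442. The probabilities of exclusion are then 0.989 and 0.956, both above 0.90. All rows of the N=30 table also reproduce.

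**How many groups can reach 30.** 9 × 30 = 270, against 161 enrolled. 161/30 = 5.4, so at most five groups hold 30 (150 subjects, leaving 11 for the other four). At least four are below 30. If 24 Part 1 subjects are set aside, 137 remain, 137/30 = 4.6, and at least five are below 30. The mean group size is 161/9 = 17.9, or 137/9 = 15.2.

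**Smallest n at which each rule still works.** A rule allowing up to k responders works when P(X≤k | n, 0.20) < 0.10, which is the same as an upper bound for k/n below 20%.

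| Rule | n | P(X≤k), true ORR 20% | Upper bound for k/n |
|---|---|---|---|
| Fewer than 2 (k=1) | 18 | 0.0991 | 19.9% |
| Fewer than 2 (k=1) | 17 | 0.1182 | 21.0% |
| 2 or fewer (k=2) | 25 | 0.0982 | 19.9% |
| 2 or fewer (k=2) | 24 | 0.1145 | 20.7% |

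For example, P(X≤1) at n=18 is 0.8^18 + 18 × 0.2 × 0.8^17 = 0.0180 + 0.0811 = 0.0991. The limits are therefore n≥18 and n≥25.

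**Groups in which the rule must fail, however the subjects were spread.**

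| Rule | 161 subjects | 137 subjects (24 Part 1 apart) |
|---|---|---|
| Fewer than 2, n≥18 | 9 × 18 = 162 > 161: at least 1 | 8 × 18 = 144 > 137: at least 2 |
| 2 or fewer, n≥25 | 7 × 25 = 175 > 161: at least 3 | 6 × 25 = 150 > 137: at least 4 |

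Setting aside only 6 Part 1 subjects (155 left) gives the same minimums as 161. Uneven accrual could add failures. Failure here means that the largest count the rule allows no longer excludes 20%. With no responders, 20% is still excluded down to n=11 (0/11: upper bound 18.9%) but not at n=10 (0/10: 20.6%).

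**Chance of wrongly excluding a true 20% ORR under the fewer-than-2 rule.**

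| n | P(X≤1), true ORR 20% | Upper bound for 1/n |
|---|---|---|
| 30 | 1.1% | 12.4% |
| 18 | 9.9% | 19.9% |
| 15 | 16.7% | 23.6% |
| 10 | 37.6% | 33.7% |

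**Interval width.** For an observed rate of 20%, the exact 2-sided 90% interval is 9% to 36% at n=30 (6/30) and 6% to 44% at n=15 (3/15).

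**The case against.** The plan's figures are correct at the size they are labelled with. The N=30 table carries its N in the title and is introduced as describing the planned cohort size. Thirty is a ceiling, the groups are described as possible, and the closures under Amendments 3 and 4 and the final total are all recorded in the protocol. Safety is the primary objective, SAP 5 says no formal hypothesis is tested, and SAP 9 contains no responder-count rule. The exact 90% and 95% intervals in SAP 9.6.1.2 will be computed on the subjects actually treated. Setting cut-offs now, in an open-label trial with closed enrolment, could also be called post hoc.

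Most of this stands and limits the harm. There is no enrolment breach, the planning arithmetic has no error, and the reported intervals will show the true precision. It does not repair a per-cohort exclusion statement that has no condition on n. SAP 9.6.1.2 also does not list the 1-sided 90% bound on which that statement rests. The post hoc objection would apply to a new threshold. It has little force against keeping the plan's own 20% threshold and its own 90% bound and evaluating them at the actual n.

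A reader might go further and infer that the exclusion fails in every group below 30, hence in at least four. The documents do not support that: a group of 18 to 29 still satisfies the fewer-than-2 rule, and one of 25 to 29 satisfies either rule. Four certain failures follow only from the synopsis rule with 24 Part 1 subjects set aside. Nor do the documents show that the fixed count will be applied to small groups. The error rates above are consequences if it is.

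**Conclusion.** The concern holds in a limited form. On the assumption that all nine reported groups enrolled someone, at least four are below 30, and no allocation of 161 subjects makes the exclusion statement true for every group. The certain failures are one group under the fewer-than-2 rule and three under the 2-or-fewer rule, or two and four if 24 Part 1 subjects are counted apart. These are minimums. The documents give neither the group sizes nor the Part 1 share, and they do not say whether Part 1 subjects are pooled into their disease group, so the true number cannot be worked out from them.

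The consequence is moderate: a misstated property of a secondary, descriptive assessment. It should be corrected because the statement is offered as the basis for judging whether an indication merits further development.

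**What to change.** In SAP 3.2, or in the CSR if the SAP is final (SAP 1 provides for documenting changes there):

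- State the achieved n in each disease group and whether Part 1 subjects are pooled into it.
- Replace the fixed count with the same criterion at the actual n: a 20% ORR is excluded only if the 1-sided exact 90% upper bound is below 20%. For groups of up to 30, this allows at most 2 responders at n=25–30, 1 at n=18–24 and 0 at n=11–17. At n≤10 exclusion is not possible, and the text should say so.
- Reconcile the fewer-than-2 wording (SAP 3.2, Protocol 5.2) with the 2-or-fewer wording (synopsis).
- Label SAP Table 3-2 as applying only to groups that reached 30.

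The cost is a few sentences and one small table, with no new subjects. The text should say that enrolment had already closed and that the threshold and confidence level are unchanged. The downside is that the stated precision becomes less favourable for the smaller groups. At n=15, for instance, excluding 20% needs zero responders, which has probability 0.95^15 = 46% if the true ORR is 5%, against 81% at n=30 with up to 2 responders allowed.
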